effect using linear contrasts from a logistic regression model. Specifically, we will use two separate Wald tests based on logistic regression, with stratification by recruitment site and baseline risk group (medium, high). Let Y_{ij} denote the primary outcome status (0=not chronic; 1=chronic) for subject i in site j , and let $Site(2)$ be an indicator variable used to code the two recruitment sites. All analyses will adjust for site and the baseline risk status represented by $RiskGroup$ (0=medium risk; 1=high risk). In order to code the treatment groups we use the variables SMT (0=no; 1=spinal manipulation therapy), and SSM (0=no; 1=supported self-management). Given interruption by COVID-19 and period of restricted randomization we will adjust for this using the variables $Period(k)$ which will be an indicator for: 1=UG3 and UH3 through March 2020; 2=calendar period of restricted randomization; and 3=calendar period of resumed full factorial randomization. Regression models for the outcome are used to structure the probability of chronic back pain as follows:

$$Additive\ Model \quad \text{logit}[P(Y_{ij} = 1 | X_{ij})] = \beta_0 + \beta_1 \cdot Site(2)_j + \beta_2 \cdot RiskGroup_{ij} + \beta_3 \cdot SMT_{ij} + \beta_4 \cdot SSM_{ij} + \beta_5 \cdot Period(2)_{ij} + \beta_6 \cdot Period(3)_{ij}$$

$$Full\ Model \quad \text{logit}[P(Y_{ij} = 1)] = \beta_0 + \beta_1 \cdot Site(2)_j + \beta_2 \cdot RiskGroup_{ij} + \beta_3 \cdot SMT_{ij} + \beta_4 \cdot SSM_{ij} + \beta_5 \cdot SSM_{ij} \cdot SMT_{ij} + \beta_6 \cdot Period(2)_{ij} + \beta_7 \cdot Period(3)_{ij}$$

Our original application proposed using an additive model to generate a single summary parameter that describes the SMT effect (β_3) and the independent SSM effect (β_4). However, the additive model uses an assumption that the effect of one intervention is independent of whether the other intervention is delivered. Such an assumption is not necessary, and a full model can be used to make inference on a single linear contrast for each treatment that represents an average treatment effect.

The “Full Model” can then be used to derive an overall or average effect of SMT, and an overall or average effect of SSM. Specifically, focusing on the effect of SMT the model yields:

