The overall SMT summary ($\beta_3 + \frac{1}{2} \beta_5$) estimates a common or average effect of SMT by pooling across sites, across risk groups, and across the two SSM arms (see figure 9.2). Similarly, $\beta_4 + \frac{1}{2} \beta_5$ estimates a common or average effect of SSM by pooling over the site, risk group, and SMT strata. Such analysis leverages the factorial design to permit separate estimates for each component of intervention. Notice that an additive model would use only 2 coefficient parameters to code the four treatment groups by assuming that the combined SMT+SSM group will have a treatment effect that is the sum of the effect for each individual component. Our analysis does not make any additive assumptions but rather directly defines a summary contrast for each treatment modality as the parameter of interest. Factorial designs are particularly efficient when evaluating two treatment modalities that work in complementary domains such as SMT (physical) and SSM (psychological) and permit separate assessment of each intervention. Formally, our primary analysis will separately test the null hypothesis $H_0: (\beta_3 + \frac{1}{2} \beta_5) = 0$ denoting no average effect of SMT, and $H_0: (\beta_4 + \frac{1}{2} \beta_5) = 0$ denoting no average effect of SSM. Each primary test will use a significance level of 0.05 without correction since each test evaluates a separate intervention. Finally, evaluation of the interaction term using $SMT_{ij} \cdot SSM_{ij}$ permits a formal evaluation for non-additivity by testing the interaction coefficient $H_0: \beta_5 = 0$ (interaction model described below).

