In 2021, the NIH statistician overseeing the trial raised the question of the adequacy of the planned adjustment for multiplicity given the trial's three main effectiveness objectives and accompanying four co-primary outcome measures. In response to this concern, the lead investigators recommended the recovery objective be changed to a key secondary outcome. Early in the conduct of the trial it was decided and approved as a protocol change to include patients that had an acute aggravation of ongoing LBP, if the ongoing pain was not rated as severe in the month prior to the aggravation. This protocol change substantially lowers the proportion of patients that can be expected to recover according to our criteria (pain severity = 0 and RMD score ≤ 2). Given this change, the recovery outcome was less appropriate as a primary effectiveness objective and demoting it to a secondary outcome mitigates the concern of cross-objective multiplicity control.

In 2022 NCCIH and the DSMB approved that the recovery effectiveness objective, formally one of the 3 primary effectiveness objectives, will be designated as a key secondary outcome.

[figure not shown]
Recovery Effectiveness Hypothesis: SMT alone will increase the rate of recovery by 5.5-7.5% or more from a baseline MC rate of 5%-15%. Similarly, SSM alone will increase the rate of recovery from 5.5-7.5%, and the combination of SMT+SSM will lead to an additive net increase in the recovery rate.

Recovery outcome definition: For a patient to be classified as recovered at the 6 month or 1 year assessment they must endorse both an NRS of 0, and an RMDQ of ≤ 2 .¹⁵² To evaluate recovery we will consider the 6-month status first and use the 1-year status second.

Recovery Analysis: The primary analysis will be two parallel tests of the average effects of SMT and SSM in a full logistic regression model for the primary outcome (recovery at 6 months). The primary analysis for recovery will use pre-specified linear contrasts for hypothesis testing regarding overall or average effects.

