Time-until-recovery: An important class of secondary analyses will consider the time-until-recovery based on measurements taken every 4 weeks during the year of follow-up. Specifically, we can define the time-until-recovery as the assessment month in which the subject is first observed to achieve an NRS=0 and RMDQ <= 2. We will use discrete time (monthly data) cumulative incidence curves to show the percent of subjects in each treatment group who have achieved a first recovery by each follow-up time period. We recognize that recovery may not be maintained, and subjects may subsequently relapse so we will also display plots showing the percent of subjects who are currently in the recovered state as a function of time. Formal comparison of cumulative incidence curves can be obtained using the log rank test since in this situation the cumulative incidence is simply 1-survival as would be computed using Kaplan-Meier curves. In addition, we will use a model-based survival analysis.

Cross-sectional outcomes at 2, 6, and 12 months: We will also conduct analysis of change in pain NRS, RMDQ, and STarT Back status from baseline. Satisfaction will also be analyzed at these

time points. This analysis will evaluate the magnitude of short, medium, and long-term effects of treatment, which are traditionally used in systematic reviews and meta-analyses.

Mediation Analysis for Psychosocial Factors: Formal mediation analysis ¹⁵⁵⁻¹⁵⁷ will focus on characterizing the degree to which self-efficacy, coping, kinesiophobia, and pain catastrophizing measured at 8 weeks can explain treatment effects at 6 months, and whether these measures obtained at 6 months explain long-term treatment effects (1 year). We will quantify the percent of the treatment effect that is explained by changes in each scale individually, and in totality when included in a multivariate model for the outcome.¹⁵⁸ We will analyze mediation for cLBP, recovery at six months and change in pain NRS and RMDQ measured at 6 months and 1 year.

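### Percent mediated for binary cLBP and recovery has no stated effect scale or interval: from logit coefficients it is not the mediated share, and at the 6-7 point cLBP effects used for power it is very imprecise

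*Combined protocol and SAP*

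**What the plan says.** Section 9, Mediation Analysis for Psychosocial Factors, plans to examine self-efficacy, coping, kinesiophobia and catastrophizing. The 8-week scores are to explain effects at 6 months, and the 6-month scores effects at 1 year. The summary measure is fixed: "We will quantify the percent of the treatment effect that is explained by changes in each scale individually, and in totality", the latter "when included in a multivariate model for the outcome". That sentence cites a reference on how much of a treatment effect a surrogate marker explains; the paragraph also cites general causal-mediation references. The outcomes are listed as follows: "We will analyze mediation for cLBP, recovery at six months and change in pain NRS and RMDQ measured at 6 months and 1 year".

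For the two binary outcomes the only models given are logistic. cLBP status is tested "using linear contrasts from a logistic regression model" (Secondary Chronicity outcome Analysis), and recovery by "two parallel tests of the average effects of SMT and SSM in a full logistic regression model" (Recovery Analysis). The mediation paragraph does not state the effect scale, the treatment contrast, an interval for the percent, the mediator-outcome confounders, or what happens when the total effect is near zero.

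**The concern.** The natural reading of a percent explained by adding scales to the outcome model is one minus the ratio of the adjusted to the unadjusted treatment coefficient. In a linear model that ratio estimates the mediated share. In a logistic model it does not, because the odds ratio is non-collapsible. Adding a variable that predicts the outcome moves the treatment log-odds away from zero even if treatment never changed that variable. The effect grows with the total prognostic strength added, so the planned model with all four scales is the most exposed.

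The ratio also divides by the total effect. For cLBP that effect is estimated with about 70% power at the smaller effect the plan considers, so the denominator is often close to zero.

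At stake is a headline percent that could be negative for an inert scale, exceed 100% by chance, or change with an analyst's choice of scale made after results are known.

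**Working it through.** **Inputs from section 9.** 1000 enrolled, 90% follow-up, allocation about 300/300/200/200 (MC, SSM, SMT, both), hence 270/270/180/180 analysed. cLBP rates are 20% under MC, 14% for each single treatment and 8% for both. Two-sided alpha 0.05 is assumed; the plan gives the level ("Each primary test will use a significance level of 0.05 without correction since each test evaluates a separate intervention") but not the sidedness. **Assumed, because the documents do not give them:** normally distributed mediators, mediator-outcome odds ratios of 1.5 to 3 per SD, correlations among scales of 0 to 0.5, and true mediated shares.

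**1. The plan's power figure.** Marginal rates:
- SSM: no SSM (270×20% + 180×14%)/450 = 17.6%; SSM (270×14% + 180×8%)/450 = 11.6%.
- SMT: no SMT (270×20% + 270×14%)/540 = 17%; SMT (180×14% + 180×8%)/360 = 11%.

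Power = Φ[(d − 1.96·s0)/s1], with d the difference in rates, s0 the pooled and s1 the unpooled standard error:
- SSM: (0.060 − 1.96×0.02354)/0.02346 = 0.59, power 72.3% (stated 72%).
- SMT: (0.060 − 1.96×0.02403)/0.02309 = 0.56, power 71.2% (stated 70%).

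The stated figures reproduce with 14% and 6 points. The chronicity power text writes 20% × 0.70 as 13% and 7 points, which is a slip.

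**2. Logit percent when nothing is mediated.** Percent = 1 − b_adj/b_tot. For 17% vs 11%, b_tot = logit(0.11) − logit(0.17) = −0.505. With a mediator of log-odds s per SD that treatment does not move, each arm's intercept a_k solves E[expit(a_k + sZ)] = p_k, with Z standard normal; b_adj is the difference of intercepts. For four scales at log-odds 0.5 each with correlation r, s = 0.5·√(4 + 12r).

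| Mediators | s | b_adj | Percent |
|---|---|---|---|
| One, OR 1.5 | 0.41 | −0.515 | −2% |
| One, OR 2 | 0.69 | −0.535 | −6% |
| One, OR 3 | 1.10 | −0.581 | −15% |
| Four, r = 0 | 1.00 | −0.568 | −12% |
| Four, r = 0.3 | 1.38 | −0.623 | −23% |
| Four, r = 0.5 | 1.58 | −0.657 | −30% |

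Recovery behaves alike. From 10% with RR 1.75, the factor-level rates are (10 + 17.5)/2 = 13.75% and (17.5 + 25)/2 = 21.25%, so b_tot = 0.526. At OR 2, b_adj = 0.563, giving 1 − 0.563/0.526 = −7%.

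**3. Non-zero shares (cLBP 17% vs 11%, one mediator, large-sample limit).** The true share on the risk-difference scale can be defined in two ways: the pure indirect effect over the total effect, or one minus the natural direct effect over the total effect.

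| Definition | OR per SD | True 25 / 50 / 75% reads |
|---|---|---|
| Pure indirect | 2 | 17 / 42 / 70% |
| Pure indirect | 3 | 10 / 38 / 67% |
| 1 − direct/total | 2 | 24 / 52 / 77% |
| 1 − direct/total | 3 | 18 / 47 / 75% |

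At OR 1.5 the second definition gives 27 / 54 / 78%, a slight overstatement. For recovery under the first definition, a true 50% reads 43-54%.

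**4. Precision (true share 50%, OR 2 per SD, pure indirect definition, 95% sampling range of the logit percent).**

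| Contrast | Analysed | Range |
|---|---|---|
| cLBP average effect, 6 points (17% vs 11%) | 540/360 | 17% to 163% |
| cLBP average effect, 7 points (16.5% vs 9.5%) | 540/360 | 20% to 129% |
| cLBP pairwise with MC, 20% vs 14% (power 37%) | 270/180 | −142% to 383% |
| Recovery average effect (13.75% vs 21.25%) | 540/360 | 24% to 147% |
| cLBP average effect, 9 points (15.5% vs 6.5%) | 540/360 | 21% to 79% |
| cLBP average effect, MC 40%, RR 0.70 (34% vs 22%) | 540/360 | 23% to 91% |

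The upper limits vary with the set-up. A separate run put the 6-7 point ranges at about 17-18% to 125-196%, and the 9-point range at about 21-102%. In the 6-point case the total effect is non-significant in about 28% of trials; in the pairwise case, in about 63%.

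**5. What a change of scale does.** For 17% vs 11% and a true share of 50%, the indirect effect estimated as a risk difference centres on the true −3.0 points, with a range of −4.5 to −1.6 (OR 2) or −4.8 to −1.3 (OR 3). The percent on that scale has median 49%, so the bias goes, but it still ranges from 26% to 161% (OR 2) or 22% to 139% (OR 3).

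**6. Continuous outcomes.** In a linear model (standardised effect 0.31, mediator-outcome correlation 0.5, 540/360) the percent is unbiased, with a range of 30% to 81%.

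**The case against.** **The plan does not name the logit ratio.** A reader might infer that the SAP prescribes a biased estimator. It does not: the paragraph states no scale and cites causal-mediation methods as well. That stands. What remains is an undefined estimand whose most natural implementation is the coefficient ratio.

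**The bias need not be downward.** A reader might infer that mediation is always understated. The zero-share result is negative whichever decomposition is used. For non-zero shares the direction depends on the decomposition and on mediator strength, and for recovery it goes either way.

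**The percent is not empty at every plausible effect.** The plan hypothesises reductions of 6-9 points from 20% or higher. At 9 points, or at a 40% MC rate, the percent is imprecise but carries information. Calling it uninformative would fit only the smaller effects and the pairwise contrasts.

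**The stated mediation objective is largely untouched.** Section 1.1, item c, concerns mediators of the primary outcomes, which are now LBP Impact, pain and RMDQ, all analysed linearly. cLBP status and recovery are secondary. The label cLBP is also loose, since primary outcome 1 is described as prevention of impactful cLBP. If the mediation paragraph means LBP Impact, the logistic issue is confined to recovery.

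**Scale is not the main source of imprecision.** Correct, as step 5 shows. Nor does showing a percent only when the total effect is significant solve it, because that selects large denominators. In 3,000 simulated trials (19% vs 12%, true share 50%) the risk-difference percent had median 49% overall but 45% among significant trials.

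**Conclusion.** The point holds as a gap in a secondary analysis, worth correcting before analysis. The plan commits to a percent explained for two outcomes modelled by logistic regression and leaves the scale, decomposition, contrast and interval open. If the percent is taken from logit coefficients, inert scales read a few points to about 15 points below zero singly, and 12 to 30 points below zero jointly. At the 6-7 point cLBP effects its sampling range runs from under 20% to well over 100%, and pairwise contrasts with MC are worse. Imprecision is the larger problem and eases as the effect grows.

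The sizes rest on the assumed mediator strengths, correlations, normality and true shares listed above. No primary test or primary outcome is affected, and the linear mediation results for pain and RMDQ do not carry this bias.

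**What to change.** Rewrite the mediation paragraph as follows.

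- **cLBP and recovery:** make natural direct and indirect effects on the risk-difference scale the mediation summary, using the causal-mediation approach already cited. Do this for each scale and for the four scales jointly. State the decomposition and the treatment contrast (average factorial effect or pairwise with MC). Give bootstrap 95% intervals.
- **Adjustment:** baseline value of the mediator, baseline pain and RMDQ, site, risk group and Period.
- **Pain and RMDQ:** report the indirect effect in scale points with an interval.
- **Any percent:** secondary, computed on the same scale as the effects, and always shown with its interval. It should not be shown only when the total effect is significant.
- **Wording:** say whether cLBP here means the binary NIH task force definition or LBP Impact.

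The cost is SAP wording and some extra computation on data already collected: the scales, pain and RMDQ are all measured at baseline under section 6. The downside is that there is no single headline percent.

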When recruitment in the UG3 phase started in October 2018 we were using the published NIH RTF new definition of chronic LBP: "a back pain problem that has persisted at least 3 months and has resulted in pain on at least half of the days in the past 6 months." Specifically, this will be assessed with two NIH RTF minimum dataset items: 1) LBP duration and 2) proportion of days that LBP has been a problem over the past 6 months.⁹⁷ The chronicity status at 12-month follow-up is based on patients' recall of their low back pain being present on more or less than half the days during the preceding 6 months.

Since the initial approval and funding of our project by NCCIH in August 2017, important published information has been accumulating regarding the importance of measuring the impact of chronic pain

including chronic LBP⁷³ (von Korff 2020, Herman 2019, Dahlhamer 2018, Dutmer 2019, Pitcher 2019). This body of literature prompted us to reevaluate the adequacy of our primary chronicity outcome measure. We were aware that the original NIH RTF chronicity outcome measure has several recognized limitations: It is a dichotomous outcome that does not incorporate pain severity, pain interference with daily activities, limitations of physical function, and is not able to quantitatively overall LBP impact. It also has limited statistical power to conduct pre-specified pairwise comparisons among the four groups. To date no data in the literature is available on the prevalence LBP chronicity using the RTF definition. The chronicity status at 12-month follow-up based on patients' recall of their low back pain being present on more or less than half the days during the preceding 6 months.

References in paragraphs above on this page:

Dahlhamer 2018 - Prevalence of Chronic Pain and High-Impact Chronic Pain Among Adults — United States, 2016. MMWR Dahlhamer J, Lucas J, Zelaya, C, et al. Morb Mortal Wkly Rep 2018;67:1001–1006.

Dutmer 2019 - The NIH Minimal Dataset for Chronic Low Back Pain Responsiveness and Minimal Clinically Important Change Dutmer, A, Reneman, M, Schiphorst Preuper, H et al. SPINE: October 15, 2019 - Volume 44 - Issue 20 - p E1211-E1218

Herman 2019 - Exploring the prevalence and construct validity of high-impact chronic pain across chronic low-back pain study samples Patricia M.Herman, Nicholas Broten et al. The Spine Journal Volume 19, Issue 8, August 2019, Pages 1369-1377

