Our primary analysis will test the global hypothesis that these three treatment comparisons are all null using a multivariate Wald test with 3 degrees of freedom and alpha=0.05. We will then provide individual confidence intervals for each coefficient that compares an intervention group to medical care based on Fishers least significant difference methods which provide individual nominal 95% confidence intervals and also estimates the simultaneous coverage probability.

Power and Sample Size for Primary Outcome of LBP Impact: To characterize the power of our primary analysis (an overall F-test) we provide a summary table that considers potential standardized mean differences comparing the individual intervention arms to medical care. For a small effect size (Cohen's d of 0.2) and an additive effect we have greater than 90% power to reject the null. However, additivity may not hold so we also consider sub-additive scenarios, and the scenario where only one intervention is effective. For small to moderate effect sizes (0.2 – 0.3 standard deviations) we have >90% with our proposed design. We assume n=1000 enrolled with a realistic 90% follow-up that yields 900 evaluated subjects. We also account for the

imbalanced design due to restricted randomization that will yield approximately 300 subjects in the UMC and SSM alone groups and 200 subjects in each of the SMT and SMT+SSM groups. Power is calculated based on 5,000 simulation replications for each scenario and presented in Table 9.1.

The current design is robust to the enrollment target and follow-up assumptions. For example, with an enrollment of n=1000 subjects and 85% follow-up we would have 90% power for our expected alternative scenario with small treatment effects (0.30 standardized mean difference) that are not additive (sub-additive 1).

A secondary evaluation will consider whether the separate effects of SMT and SSM are potentially additive and this will be done using a formal test for interaction:

$$\text{Interaction Model: } E(Y_{ij} \mid X_{ij}) = \beta_0 + \beta_1 \cdot \text{Site}(2)_j + \beta_2 \cdot \text{RiskGroup}_{ij} + \beta_3 \cdot \text{SMT}_{ij} + \beta_4 \cdot \text{SSM}_{ij} + \beta_5 \cdot \text{SMT}_{ij} \cdot \text{SSM}_{ij} + \beta_6 \cdot \text{Period}(2)_{ij} + \beta_7 \cdot \text{Period}(3)_{ij}$$

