Power and Sample Size for Secondary Outcome of Chronicity: In order to determine the necessary sample size for effectiveness evaluation we need to formulate assumptions for the binary secondary outcome rate in the treated and untreated groups. [name] and Shekelle³⁴ review six studies conducted in primary care that focused on pain, functional status, or mixed outcomes. Using results from this paper we conservatively assume a rate of cLBP of 20% at 1 year. In order to formulate appropriate effect estimates we consider detection of a relative risk of RR=0.70 for each of SMT and SSM individually implying a reduction of the rate from 20% to 14% for these intervention groups. Based on the Cochrane Back Review Group¹⁴⁸ a relative risk of 0.70 is a clinically relevant and medium in size intervention effect, while the assumption of additive effects on the probability scale would lead to a cLBP rate of 8% among those randomized to SMT+SSM, which is considered a “large” treatment effect (RR=0.40). Therefore, we seek to design our study to detect and medium sized treatment effects, and consider power under a collection of plausible scenarios. A recent cohort study of acute LBP patients in primary care reported a similar proportion of patients with cLBP at 2 years, but noted the estimate varied based on the case definition¹⁴⁹ and estimates based on the NIH RTF definition are not yet available. Relative to general LBP patients, we expect a rate of chronicity in the MC group to be larger since we are enrolling subjects at an increased risk of chronicity. Accordingly, we increased the estimated proportion with cLBP in the MC group to be 30 and 40% and determined the magnitude of treatment effects for which we have $\geq 80\%$ power. At 1 year, we assume that we will have at least 88% follow-up based on prior studies conducted at the clinical research sites and studies^{11 150} with similar incentives¹⁵¹. Thus, with n=1000 enrolled subjects we expect at least n=880 total subjects available for primary analysis.

Our original sample size was chosen as n=1180 (since modified to n=1000) to ensure 80% power assuming an additive model with a chronic rate of 20% in UMC and a medium relative risk (RR) of 0.70. To evaluate power we conducted simulations using the R statistical package. We generated data under various additive assumptions. For analysis we first considered a single

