likelihood ratio test of one treatment modality (either SMT or SSM). For simulations we considered crude analysis while our formal analysis will additionally adjust for site and baseline risk and therefore improve power since these are variables that only predict outcome and are not related to treatment group. For each scenario we simulated 5,000 data sets and empirically calculated power as the percentage of replicates in which the null hypothesis was rejected.

Using simulations with n=1000 subjects, 90% follow-up, and accounting for our imbalanced allocation due to COVID interruption we compute power for analyses that consider individual marginal treatment effects for both SMT and SSM. If we assume a UMC chronicity rate of 20% and a relative risk of 0.65 (rate under treatment = $20\% * 0.65 = 13\%$, or an absolute risk reduction of 7%) then we have >85% power to detect average SSM or SMT effects. If we a smaller effect corresponding to a relative risk of 0.70 (rate under treatment = $20\% * 0.70 = 13\%$, or an absolute risk reduction of 7%) then we have approximately 70% power to detect average SSM or SMT effects of this magnitude (specifically accounting for imbalance power is 72% for SSM and 70% for SMT). Power is greater for any relative risk when the UMC rate is increased to 30% or 40%. These relative risk effect sizes equate to medium effect sizes and are considered clinically important by Cochrane's Back Review Group.¹⁴⁸ We have not powered the study to detect interaction for the binary chronicity endpoint, but rather have powered the study to detect interaction on the underlying function and disability scales (see below).

Furthermore, we have excellent power to detect interaction effects where the effect of SMT and SSM may be synergistic or antagonistic, and using alpha=0.05 we have >80% to detect a X-point difference in LBP Impact treatment effects of one modality across the strata defined by the other treatment modality.

Secondary Effectiveness Outcome of Recovery: Determine the effectiveness of SMT, SSM, and the combination of SMT+SSM relative to medical care (UMC) in promoting recovery from acute or subacute LBP at 6 months.

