Factorial Model Assumptions: We have assumed both an additive data-generating model with small effects and alternative sub-additive scenarios with moderate effects for the three primary effectiveness outcomes. However, for the secondary binary outcomes and we have assumed additivity to assess power for SMT and SSM treatment main effects. For these binary outcomes it is possible that there is an interaction that is either synergistic or antagonistic (sub-additive). In this situation our proposed analysis will estimate an average treatment effect rather than a common treatment effect. A synergistic interaction however would suggest that SMT + SSM produce greater effects together, than when used alone. Conversely, an antagonistic interaction would suggest that their effects are less than additive. Both scenarios would provide new and important information and advance what is known about these therapies and how they should be applied for acute and sub-acute LBP. Importantly, even if an interaction is observed, we have >80% power to detect the following differences between the combined group or either of the single interventions alone compared to medical care: For prevention of chronicity, we will be powered to detect a reduction of 9% (RR=0.55) at an event rate of 20% in the MC group, a reduction of 11% (RR=0.63) if the event rate is 30%, and a reduction of 12% (RR=0.7) if the event rate is 40%. For recovery, we will be powered to detect an increase of 7% (RR=2.4) at an event rate of 5% in the MC group, 9% (RR=1.9) if the event rate is 10%, and 10% (RR=1.67) if the event rate is 15%.

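### At n=1000 the claimed >80% power against medical care on chronicity and recovery holds only for SSM alone; for SMT alone and SMT+SSM it is about 72–77%

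*Combined protocol and SAP*

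**What the plan says.** The paragraph on Factorial Model Assumptions (section 9, Potential Problems & Alternative Strategies) addresses an interaction between SMT and SSM on the binary secondary outcomes. It states that "we have >80% power to detect the following differences between the combined group or either of the single interventions alone compared to medical care". The differences listed are:

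- chronicity: reductions of 9, 11 and 12 points from MC rates of 20%, 30% and 40%
- recovery: increases of 7, 9 and 10 points from MC rates of 5%, 10% and 15%

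No sample size, follow-up rate, alpha or test is given there.

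The current design is set out under Power and Sample Size for Primary Outcome of LBP Impact: "We assume n=1000 enrolled with a realistic 90% follow-up that yields 900 evaluated subjects". The same paragraph describes an "imbalanced design due to restricted randomization that will yield approximately 300 subjects in the UMC and SSM alone groups and 200 subjects"; the figure of 200 applies to SMT and to SMT+SSM alike. The chronicity power section uses a similar follow-up rate: "At 1 year, we assume that we will have at least 88% follow-up based on prior studies".

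The marginal chronicity power was updated for this design: "Using simulations with n=1000 subjects, 90% follow-up, and accounting for our imbalanced allocation due to COVID interruption we compute power". For a relative risk of 0.70 that paragraph prints a treated rate of 13%, "or an absolute risk reduction of 7%) then we have approximately 70% power to detect average SSM or SMT effects of this magnitude". The preceding text describes the same relative risk as "implying a reduction of the rate from 20% to 14% for these intervention groups".

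**The concern.** The power claim covers all three active arms against MC, but the COVID-period restricted randomization left the two SMT-containing arms about a third smaller than MC and SSM. A set of differences that just reaches 80% power for one comparison should not reach it for the others.

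This paragraph is where the plan gives power for individual arms on chronicity and recovery; the other binary power statements are marginal. It is also offered as the assurance for the case of interaction, when an averaged effect is least informative. Section 3.2 already concedes, as a weakness of the dichotomous chronicity outcome, that "It also has limited statistical power to conduct pre-specified pairwise comparisons among the four groups". If the claim is wrong, a null SMT-arm result on either outcome could be read as coming from an adequately powered comparison.

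The 13% in the chronicity paragraph raises a smaller problem. As printed, the relative risk 0.70 case is identical to the 0.65 case just before it (13%, 7 points), so one effect carries both more than 85% power and about 70% power.

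**Working it through.** **Inputs.** The six pairs of rates come from the Factorial Model Assumptions paragraph. Enrolment by arm (300 MC, 300 SSM, 200 SMT, 200 SMT+SSM) comes from the LBP Impact power section; these sum to 1000, so they are enrolled and not evaluable counts. At 90% follow-up they become 270, 270, 180 and 180. Alpha is taken as two-sided 0.05. That is an assumption for these contrasts, because the plan states 0.05 without correction only for the marginal tests. The calculation is crude (unadjusted), as the plan's own binary simulations were.

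**Formula.** Pooled two-proportion z-test:

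power = Φ[(|p1 − p2| − 1.96 × SE0) / SE1]

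SE0 = √[p̄(1 − p̄)(1/n1 + 1/n2)], with p̄ the pooled rate; SE1 = √[p1(1 − p1)/n1 + p2(1 − p2)/n2].

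**Reproducing the plan's figure.** The claim reproduces at 295 × 0.88 = 259.6 per arm, the balanced n=1180 allocation with 88% follow-up: 81.1–83.2% across the six pairs. That this is where the figures came from is an inference.

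**Worked example, chronicity 20% vs 11%, 270 MC vs 180 SMT.** p̄ = (270 × 0.20 + 180 × 0.11)/450 = 0.164. SE0 = √[0.164 × 0.836 × (1/270 + 1/180)] = 0.03563. SE1 = √[0.16/270 + 0.0979/180] = 0.03371. Power = Φ[(0.09 − 1.96 × 0.03563)/0.03371] = Φ(0.598) = 72.5%.

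**All six pairs (power, %):**

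| Outcome, MC vs active | 259.6/259.6 | SSM vs MC 270/270 | SMT or SMT+SSM vs MC 270/180 |
|---|---|---|---|
| Chronicity 20 vs 11 | 81.1 | 82.6 | 72.5 |
| Chronicity 30 vs 19 | 83.2 | 84.6 | 75.3 |
| Chronicity 40 vs 28 | 82.5 | 83.9 | 74.8 |
| Recovery 5 vs 12 | 81.8 | 83.2 | 75.9 |
| Recovery 10 vs 19 | 83.1 | 84.6 | 76.9 |
| Recovery 15 vs 25 | 81.5 | 83.0 | 74.8 |

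**Sensitivity to follow-up, SMT arms vs MC.** 88% (264/176): 71.5–76.0%. 85%, the plan's own robustness case (255/170): 70.0–74.6%. Complete follow-up (300/200): 77.1–81.0%. SSM alone stays above 80% at 88% (81.7–83.8%) and at 85% (80.4–82.5%).

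**Sensitivity to the test at 270/180.** Exact Pearson 73.1–77.3%; exact likelihood-ratio 74.3–76.9%; exact logistic Wald 72.5–77.1%; unpooled 71.7–77.7%; continuity-corrected 68.2–73.4%. No two-sided version reaches 80%.

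**Size of the shortfall.** With 270 in MC, an SMT arm needs between 209 and 240 evaluable participants for 80% power, depending on the pair, against 180. Solving the formula for 80% power gives these detectable differences in points:

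| | Chronicity at MC 20/30/40% | Recovery at MC 5/10/15% |
|---|---|---|
| Stated | 9 / 11 / 12 | 7 / 9 / 10 |
| SMT or SMT+SSM vs MC (270/180) | 9.7 / 11.6 / 12.7 | 7.5 / 9.4 / 10.7 |
| SSM vs MC (270/270) | 8.7 / 10.4 / 11.4 | 6.65 / 8.4 / 9.6 |

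**The 13% figure.** 0.20 × 0.70 = 0.14. To see whether the rate or the power is misprinted, take effects additive on the probability scale and compare margins (SMT: 540 without vs 360 with; SSM: 450 vs 450). For SMT at 14% the marginal rates are (0.20 + 0.14)/2 = 0.17 and (0.14 + 0.08)/2 = 0.11. Power is 71.2% for SMT and 72.3% for SSM, against the stated 70% and 72%. At 13% it is 86.1% and 86.4%, matching the stated more than 85%. So the rate is misprinted and the power is right. The agreement also supports the 270/180 reading of the design.

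**The case against.** The paragraph is a contingency remark, not the sample-size justification. Both outcomes are secondary and are tested mainly by marginal contrasts; the detectable differences move by less than a point; no test, estimand or sample size changes. A reader of section 9 already sees marginal power of only 70–72% at a relative risk of 0.70, and section 3.2 admits weak pairwise power. All of this stands and limits the consequence, but it does not make the stated power correct.

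Recovery is assessed first at 6 months, and no 6-month follow-up rate is given, so using 90% there is an assumption. Complete follow-up is the upper bound: 80.0%, 81.0% and 79.0% for the three recovery pairs. The recovery shortfall is therefore softer than the chronicity one, which persists even at 300/200 (77.1%, 79.7%, 79.2%).

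The final model adjusts for site and risk group, which the plan expects to raise power. It also adjusts for period, which works the other way for the SMT arms because restricted-period MC participants have no concurrent SMT participants. As an illustration only, assume 90 evaluable participants each in MC and SSM from the restricted period, (300 − 200) × 0.9. A period-adjusted logistic Wald calculation without site and risk group gives about 66–73% for the SMT arms, and SSM alone still exceeds 80%. Adding risk group, with an assumed odds ratio of 1.5–5 and 25–50% at high risk, gives about 67–76%. The net effect of the full model depends on inputs the plan does not give, so the crude figures carry the conclusion.

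A one-sided test at 0.05 would give 82.4–85.0% at 270/180, but the plan states no one-sided test.

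**Conclusion.** The concern holds. Under the plan's current allocation and 90% follow-up, power above 80% is supported for SSM alone against MC but not for SMT alone or SMT+SSM, where the six listed differences have 72.5–76.9% crude power. This rests on a two-sided 0.05 test, on 300/200 being enrolled counts, and on 90% follow-up applying to both outcomes.

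The 9-point chronicity reduction at a 20% MC rate is the top of the plan's hypothesised 6–9 points for SMT alone, so at that rate SMT alone against MC falls short of 80% throughout the hypothesised range. A fully additive combined effect (8% vs 20%) would still have about 95% power at 270/180. Primary-outcome power is unaffected. The 13% and 7-point figures for a relative risk of 0.70 are a separate misprint.

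**What to change.** In Factorial Model Assumptions, state the sample size, follow-up, alpha and test, and replace the single list with one list for each type of comparison at n=1000. On the crude basis above, the 80%-power differences are:

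- SMT alone or SMT+SSM vs MC: about 9.7, 11.6 and 12.7 points for chronicity and 7.5, 9.4 and 10.7 points for recovery
- SSM alone vs MC: about 8.7, 10.4 and 11.4 points for chronicity and 6.65, 8.4 and 9.6 points for recovery

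Give the 6-month follow-up assumed for recovery. Note that the period adjustment by itself lowers power for the SMT-arm comparisons but not for SSM alone; preferably recompute under the planned model with the actual enrolment by period.

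In the chronicity power paragraph, change 13% and 7% for a relative risk of 0.70 to 14% and 6 points, and keep the stated power.

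The cost is SAP wording and a short recalculation. No participants are added and no analysis changes; the stated secondary-outcome power for the SMT arms becomes less favourable.
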